6.3 Secondary outcomes analysis

Our approach to analysis of secondary outcomes will mirror the approach outlined above for primary outcome analysis.

The secondary outcomes are that boys:

- Get along better with their peers, measured by the Strengths and Difficulties Questionnaire (SDQ) peer relationship problems sub-scale.
- Get along better with their teachers, measured by the SCQ teacher bonding and attachment subscale.
- Reduced behavioural difficulties, measured by the SDQ externalising behaviours score.

- Reduction in emotional symptoms, measured by the SDQ emotional symptoms subscale.
- Have positive relationships with their project co-ordinator (treatment group) / significant adult (control group), measured by the Social Support and Rejection Scale.

About the Strengths and Difficulties Questionnaire (Goodman 1997).

The SDQ is a 25 item questionnaire measuring behaviours, emotions and relationships for 4 to 17 year olds. It contains 5 subscales:

- 1. Emotional symptoms.
- 2. Conduct problems.
- 3. Hyperactivity/inattention.
- 4. Peer problems.
- 5. Prosocial behaviour.

Each item is scored on a 3 point Likert scale from 0 to 2, such that the scores for each subscale ranges from 0 to 10. For the prosocial values subscale high scores are desirable (e.g., greater prosocial values), but for the other subscales (e.g., emotional symptoms subscale, conduct problems subscale, peer relationship subscale) high scores are not desirable (e.g., greater emotional problems, greater conduct problems, poorer peer relationships). The total difficulties score ranges from 0 to 40 and is the sum of subscales 1) to 4) above. The externalising behaviours score ranges from 0 to 20 and is the sum of the conduct and hyperactivity scores. Items from the impact supplement on overall distress and impairment generate an impact score, which ranges from 0 to 10.⁵

For each secondary outcome, we will conduct analysis of impact on the measures outlined above. This will be conducted using the same model specified for the primary outcomes measure in section 6.2 above, which will include the baseline measurement for the respective secondary outcome variable. In addition, as discussed in section 6.2 above, we will also run this analysis on the three individual subscales of the SCQ.

This analysis is designed to evaluate the differences in peer relationships, teacher relationships, emotional symptoms, behaviour, and positive relationships between the young

⁵ Further information about the SDQ can be found on the YEF website here: https://youthendowmentfund.org.uk/wp-content/uploads/2022/04/18.-YEF-SDQ-guidance-April-2022.pdf

person and their project co-ordinator between those in the BDP group, and those in the business-as-usual group.

We will also run robustness checks to assess the underlying assumptions for ANCOVA for each secondary outcome measure. This will include assessing normality of the data using histograms and K-S tests. If the data does not meet these assumptions, we will run a non-parametric ANCOVA analysis. This will be determined once all data has been collected.

This analysis will be conducted in SPSS.

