		Relationships with teachers, measured by the School Connectedness Teacher Bonding and Attachment subscale (Marsh and Randolph, 2020).		

¹ Please note at baseline, we will not be using the Social Support and Rejection Scale as the young person will not have worked with the project co-ordinator prior to the BDP.

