4.3 Outcomes

The primary outcome measure for the evaluation is school engagement measured by the School Connectedness Questionnaire (Marsh and Randolph, 2020). This measure was selected from the YEF outcomes framework in collaboration with YEF and Future Men colleagues.²

The secondary outcomes are that boys:

- Get along better with their peers, measured by the Strengths and Difficulties Questionnaire (SDQ) peer relationship problems sub-scale.
- Get along better with their teachers, measured by the SCQ teacher bonding and attachment subscale.
- Reduced behavioural difficulties, measured by the SDQ externalising behaviours score.

² For more information see: https://youthendowmentfund.org.uk/outcomes/.

- Reduction in emotional symptoms, measured by the SDQ emotional symptoms subscale.
- Have positive relationships with their project co-ordinator (control group) / significant adult (treatment group), measured by the Social Support and Rejection Scale total score.

Data for all measures is collected directly from boys by Future Men's research assistants and/or a project co-ordinator who is not delivering support using an online survey software. This is administered at baseline, 12 weeks and 24 weeks post-randomisation.

5 Sample size calculations

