6.5 Further analyses

We will conduct the following exploratory further analysis:

• The impact of positive relationships. We will evaluate the extent to which positive relationships between the young person and project co-ordinator (treatment group) or significant adult (control group) influenced the primary outcome over and above the impact of the BDP through the SSRS. We are proposing conducting this analysis because the theory of change suggests that the key mechanism of change for the BDP is that it has its effect through an increase in positive relationships with a trusted adult. This will take a mediation analysis approach, i.e. we will estimate the direct and indirect effects, following the approach outlined in Gunzler et al. (2013).

About the Social Support and Rejection Scale

The SSRS has 4 dimensions: Feels valued, trust, mentoring, and negativity. Each item is scored from 1 (never) to 5 (always). Each subscale score is the average of items that make up the subscale. Higher scores on the negativity scale reflect higher levels of stress and negativity within the relationship. For the overall scoring of the scale a high score represents a positive relationship.

• Improvements to school attendance and reductions to exclusion as measured by school administrative data. If we are able to access school administrative data which is of sufficient high quality, consistency and comparability across schools, we will explore whether there is a difference in attendance and exclusions between those in

the BDP group and those in the business-as-usual group. This will follow the same model as set out for the primary and secondary outcomes analysis.

• **Dosage and fidelity.** Any analysis relating to dosage and fidelity will be exploratory in nature. If power calculations suggest that the analysis will be sufficiently powered, we will explore the association between the level of dosage and the impact on the SCQ. This data will be captured by monitoring data on number of sessions received collected by the Future Men delivery team. This analysis will be conducted using a general linear model assuming normality, or a generalized linear model. It will answer questions such as: does attending 8 or more BDP sessions result in a similar impact as attending all 12 sessions?

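### SAP 6.3 gives the Social Support and Rejection Scale a model with a baseline that is not collected, and because the arms rate different adults, neither its contrast nor the 6.5 mediation can be read as a BDP effect

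*SAP*

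**What the plan says.** **Model.** SAP 6.3 carries the 6.2 ANCOVA (outcome on own baseline, group and school) over to each secondary outcome, "which will include the baseline measurement for the respective secondary outcome variable". The SSRS is in that list, and no exception is made for it.

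**Baseline.** The footnote to Table 1 in 4.1 says that "at baseline, we will not be using the Social Support and Rejection Scale", because the boys will not yet have worked with a co-ordinator. The baseline rows of Table 1 leave the SSRS out accordingly. Section 4.3, speaking of all measures, says: "This is administered at baseline, 12 weeks and 24 weeks post-randomisation".

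**Adult rated.** Section 4.3 has "project co-ordinator (control group) / significant adult (treatment group"; 6.3 has "project co-ordinator (treatment group) / significant adult (control group". Section 6.5 agrees with 6.3. The closing sentence on the purpose of the 6.3 analysis then describes the SSRS comparison as one of boys' relationships with their co-ordinator, BDP against business as usual.

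**Mediation.** Section 6.5 will examine how far "positive relationships between the young person and project co-ordinator (treatment group) or significant adult (control group) influenced the primary outcome", by estimating direct and indirect effects through the SSRS. Its reason is that the theory of change makes a better relationship with a trusted adult the key mechanism of the programme.

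**Status.** Section 6.5 labels its analyses exploratory, and 6.9 describes all secondary and further analyses as tentative and exploratory.

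**The concern.** Three defects meet on one outcome, and they differ in weight.

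- The specified model contains a covariate that will not exist for the SSRS. An analyst following 6.3 has to improvise after seeing the data.
- The two arms answer the questionnaire about different people. A difference between arms may come from the programme, from the change of person, or from both. Reported as 6.3 describes it, it would be presented as an effect on the co-ordinator relationship in both groups, although under 6.3 and 6.5 the control boys rate someone else.
- Section 4.3 contradicts 6.3 and 6.5 on which arm rates whom.

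The second matters most. The SSRS is also the mediator in 6.5, so the report's statement on whether BDP works through its stated mechanism would rest on a score whose meaning changes with allocation.

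**Working it through.** **1. Can the 6.3 model be fitted to the SSRS?** The 6.2 model is Y = β0 + β1·Baseline + β2·Group + school terms + error. For the SSRS, Baseline would be the pre-randomisation SSRS score, which the Table 1 footnote says is not taken. As written, the model cannot be fitted. Without β1·Baseline it can, and randomisation still supports the comparison of scores by arm.

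**2. What does the missing baseline cost?**

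Inputs from SAP section 5: two-sided alpha 0.05, power 0.80, pre/post correlation 0.7 (set for the primary outcome), 1:1 allocation, 422 boys planned, 424 after the March 2025 update.

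Formula: MDES = M·√[(1 − R²)/(P(1 − P)N)], with P = 0.5, R² = 0.7² = 0.49 and M = t(0.975) + t(0.80) ≈ 2.808.

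The plan's own figure first:
- N = 422: 2.808·√(0.51/105.5) = 0.195.
- N = 424: 2.808·√(0.51/106) = 0.195.

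Both reproduce Table 2. For the SSRS, R² = 0:
- N = 424: 2.808·√(1/106) = 0.273.

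By the normal approximation, power at 212 per arm for a difference of 0.195 SD falls from 0.80 to 0.52, and 413 per arm would be needed to restore an MDES of 0.195. If another baseline score served as covariate, with an assumed correlation of 0.3 to 0.5, the MDES would be 2.808·√(0.91/106) = 0.260 down to 2.808·√(0.75/106) = 0.236.

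**3. What does the group coefficient estimate?** Write S_T and S_C for mean SSRS in the BDP and control arms, with the adult rated in brackets. Under 6.3 and 6.5,

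β2 = S_T(co-ordinator) − S_C(significant adult)
= [S_T(significant adult) − S_C(significant adult)] + [S_T(co-ordinator) − S_T(significant adult)].

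The first bracket is a programme effect on one common relationship. The second, δ, is the difference between rating the two adults. The plan does not have BDP boys rate a significant adult, so S_T(significant adult) is never observed. Allocation and adult rated are fully aliased, and neither sample size nor covariate adjustment separates them.

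**4. What happens to the mediation?** Take the simplest linear form, with a for group to mediator and b for mediator to outcome, and suppose that the change of adult only shifts the score by δ. The estimated indirect effect is then (a + δ)·b, and the direct effect moves by −δ·b. The total effect is unchanged, but its split into direct and indirect parts, which is what 6.5 is for, is off by δ·b.

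**5. Which sections conflict?**

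| Item | One reading | Other reading |
|---|---|---|
| SSRS at baseline | Not used: 4.1 footnote, Table 1 baseline rows | All measures given: 4.3; own baseline in the model: 6.3 |
| Who rates the co-ordinator | BDP arm: 6.3, 6.5 | Control arm: 4.3 |
| Adult in the SSRS contrast | Differs by arm: 4.3, 6.3 list, 6.5 | Co-ordinator in both: end of 6.3 |

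On the labels 4.3 stands alone, and the Table 1 footnote also ties the co-ordinator to the BDP.

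**The case against.** The strongest reply is that the construct is wider than the co-ordinator: 6.5 speaks of a trusted adult, so comparing each boy's relationship with the adult named for his arm is a reasonable summary. Part of this stands. Such a comparison can be described. It does not rescue the causal reading, because 6.5 states the mechanism as an increase in positive relationships. With no baseline, and no rating by BDP boys of other adults, an increase is not measured.

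A second reply is that these analyses are labelled exploratory. That lowers the weight of the point, but a label does not identify an effect that the design leaves aliased.

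A third is that 6.1 calls the analysis plan a draft, to be finalised once baseline data are in. Version 1.1 followed the end of baseline collection, and its version history records only the sample-size update in section 5.

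Stronger readings go too far:

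- A reader might infer that the SSRS cannot be analysed at all, or that nothing about it is interpretable. The documents do not support this. A model with group and school can be fitted, and a descriptive comparison remains.
- A reader might take the reversed labels as a threat to the estimates. They look like a drafting slip in 4.3.
- A reader might put a size on δ, or say that the sign of the effect would be wrong. The SAP does not say who the significant adult is or how that person is selected, and it gives no figure for the difference. Both size and direction are unknown.

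**Conclusion.** The SSRS analysis is wrong as written in 6.3 and 6.5, in three respects of unequal weight.

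- **Differing adult (serious).** The between-arm difference and the indirect effect carry an unidentified component. They cannot be read as effects of BDP on a common relationship, or as a test of its mechanism. Step 4 above assumes a linear model and a constant shift; the aliasing itself needs neither assumption.
- **Missing baseline (specification error).** The stated model cannot be fitted. The loss is of precision, not validity: MDES 0.273 against 0.195 at 212 per arm. This takes school as explaining none of the SSRS variance, and every boy in the projected sample of 424 as giving an SSRS score. It says nothing about the size of the referent problem, which is one of bias.
- **Section 4.3 (drafting).** It contradicts other sections on arm labels and on baseline collection.

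The primary School Connectedness analysis is unaffected. The plan should be corrected before the SSRS is analysed, in keeping with the exploratory status of these results.

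**What to change.** 1. Reconcile 4.3 with the Table 1 footnote, 6.3 and 6.5, both on whether the SSRS is given at baseline and on which arm rates which adult.
2. In 6.3, give the SSRS its own model with group and school and no SSRS baseline. Another baseline score already collected may be added as a covariate if it is named now. State the MDES of about 0.27 SD at 212 per arm.
3. Correct the closing sentence of 6.3 so that it names the adult rated in each arm.
4. In 6.3 and 6.5, state that the SSRS difference between arms and the indirect effect through the SSRS are descriptive, and will not be read as causal effects of BDP on a common relationship or as a test of the mechanism.
5. Optional: add a within-BDP association of the 12-week SSRS with 24-week school connectedness, labelled non-causal. It puts the mediator before the outcome and keeps one type of adult, but it gives up randomisation and uses about half the sample (212 at 12 weeks, before any later loss). It should supplement the planned analysis; the correction does not depend on it.

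Items 1 to 4 change wording only and need no new data. The sponsor gives up a causal SSRS claim and a causal indirect effect, neither of which the data could support.

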6.4 Subgroup analyses

The subgroup analyses we plan to undertake are likely to be exploratory in nature. Before undertaking sub-group analyses we will assess whether these would be sufficiently powered based on the data we have collected. If power calculations show that this analysis is underpowered, the analysis will be reported as exploratory, and caveated that results should be interpreted with caution.

We will assess the presence of heterogenous treatment effects in line with race equity, equality, diversity and inclusion considerations. There is limited evidence about the effectiveness of school-based interventions which aim to reduce exclusions for those from racially minoritised backgrounds. As such, we will explore whether the BDP was equally effective for those from racially minoritised backgrounds compared to those from White British backgrounds. This would likely be an underpowered analysis so caution should be applied when interpreting the results.

We will conduct this analysis by exploring the presence of interaction effects between ethnicity and treatment allocation. We will report the estimated differences across subgroups with the respective confidence intervals. This would use the following model:

$$\begin{split} Y_i &= \beta_0 + \ \beta_1 Baseline_i + \beta_2 Group_i + \gamma School_k + \delta Ethnicity_{ij} + \theta Ethnicity_{ij} * Group_i \\ &+ \ \varepsilon_i \ \epsilon \ N(0, \ \sigma^2) \end{split}$$

For i = 1, ..., n pupils per school, with j = 1, ..., J ethnicities, at k = 1, ..., K schools

This model uses the same variables as the model set out in section 6.2. In addition:

- *Ethnicity*_{*ij*} is a vector of binary dummy variables for J 1 ethnicities.
- θ is a vector of parameters indicating the existence of heterogenous treatment effects by ethnicity. The total treatment effect for boys in each ethnicity grouping will be $\beta_2 + \theta$.

We will report both the point estimates and confidence intervals for θ . If θ indicates that the BDP is differentially impactful for different ethnicities, we will also consider re-running the model in section 6.2 for each sub-group separately (i.e. for boys from White, Asian, Black, Mixed and Multiple ethnic backgrounds, and Other ethnic backgrounds). If the two treatment effects are similar, this will strengthen the findings from this exploratory analysis.

We will also conduct exploratory subgroup analyses on Free School Meal (FSM) eligibility. We will include power calculations for this analysis in the final report, once the sample size for this subgroup is confirmed. However, this analysis will likely be underpowered, so results should be interpreted with caution. We will take the same approach to this analysis as outlined for ethnicity above.

In addition, based on assessment of statistical power, we may explore subgroup analyses for English as an Additional Language (EAL), and special educational needs and disability status (SEND). This analysis will be conducted on demographic data provided by school partners, and will also take the same approach as outlined for ethnicity above.

6.5 Further analyses

We will conduct the following exploratory further analysis:

• The impact of positive relationships. We will evaluate the extent to which positive relationships between the young person and project co-ordinator (treatment group) or significant adult (control group) influenced the primary outcome over and above the impact of the BDP through the SSRS. We are proposing conducting this analysis because the theory of change suggests that the key mechanism of change for the BDP is that it has its effect through an increase in positive relationships with a trusted adult. This will take a mediation analysis approach, i.e. we will estimate the direct and indirect effects, following the approach outlined in Gunzler et al. (2013).

About the Social Support and Rejection Scale

The SSRS has 4 dimensions: Feels valued, trust, mentoring, and negativity. Each item is scored from 1 (never) to 5 (always). Each subscale score is the average of items that make up the subscale. Higher scores on the negativity scale reflect higher levels of stress and negativity within the relationship. For the overall scoring of the scale a high score represents a positive relationship.

• Improvements to school attendance and reductions to exclusion as measured by school administrative data. If we are able to access school administrative data which is of sufficient high quality, consistency and comparability across schools, we will explore whether there is a difference in attendance and exclusions between those in

the BDP group and those in the business-as-usual group. This will follow the same model as set out for the primary and secondary outcomes analysis.

• **Dosage and fidelity.** Any analysis relating to dosage and fidelity will be exploratory in nature. If power calculations suggest that the analysis will be sufficiently powered, we will explore the association between the level of dosage and the impact on the SCQ. This data will be captured by monitoring data on number of sessions received collected by the Future Men delivery team. This analysis will be conducted using a general linear model assuming normality, or a generalized linear model. It will answer questions such as: does attending 8 or more BDP sessions result in a similar impact as attending all 12 sessions?

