	6.1	Overview	12		
	6.2	Primary outcome analysis	13		
	6.3	Secondary outcomes analysis	14		
	6.4	Subgroup analyses	16		
	6.5	Further analyses	17		
	6.6	Interim analyses and stopping rules	18		
	6.7	Longitudinal follow-up analyses	19		
	6.8	Imbalance at baseline	19		
	6.9	Missing data	20		
	6.10	Compliance	21		
	6.11	Intra-cluster correlations (ICCs)	22		
	6.12	Presentation of outcomes	22		
7	Ref	erences	23		

3 Introduction

This is the statistical analysis plan for an efficacy study, two-arm parallel randomised control trial (RCT) evaluation and implementation and process evaluation (IPE) of Future Men's Boys Development Programme (BDP). The BDP will be delivered across six schools in South London between September 2023 and July 2025 i.e. across two academic years. The efficacy study will run until March 2026.

The BDP is a targeted, manualised, social and emotional learning programme delivered across 12 one-to-one, 50 to 60-minute-long sessions. It aims to develop the social and emotional capacity and skills of boys in Years 7-11 who are at risk of exclusion and disengagement from schools, to improve school engagement and reduce the likelihood of exclusion.

The evaluation team are collecting a range of data throughout the trial. This includes:

- Self-reported outcomes measures, including the School Connectedness Questionnaire, the Strengths and Difficulties Questionnaire, and the Social Support and Rejection Scale.
- Demographic data provided by school partners, including age, sex, Free School Meal (FSM) eligibility, special educational needs and disabilities (SEND) data, English as an Additional Language (EAL) and care status.
- Activity and monitoring data collected by the Future Men delivery team.

This document sets out our planned analysis for each data type in more detail. The rest of this document is structured in the following way:

- Section 4: Trial design sets out the research questions, key outcomes and measures, and randomisation approach for the trial.
- Section 5: Sample size calculations presents the power calculations for the trial.
- Section 6: Analysis sets out the approach to analysis of primary outcomes, secondary outcomes, subgroup analysis, longitudinal analysis, further and interim analysis, missing data, compliance and outcomes presentation.

4 Trial design

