6.2 Primary outcome analysis

The primary outcome is an improvement in school engagement at the individual level, as measured by the School Connectedness Questionnaire (SCQ). All young people will have completed the SCQ before randomisation, and at around 12 weeks and 24 weeks post randomisation. The primary outcome time point is 12 weeks post-randomisation.

About the School Connectedness Questionnaire (Marsh and Randolph, 2020)

The SCQ contains 10 items. Each item is marked either Not True, Somewhat True, or True, which are assigned a score of 1 to 3 respectively. It consists of three subscales:

- 1. Teacher bonding and attachment (3 items);
- 2. Peer bonding and attachment (4 items); and
- 3. School engagement (3 items).

The score for each subscale is the sum of its items. The primary outcome measure for this trial is the sum of the three subscale scores, and analysis of each subscale score will also be presented separately.

There is considerable debate about best practice when it comes to the analysis of data from RCTs. For example, Twisk et al. (2018) advocate for utilising longitudinal analysis of covariance or a repeated measures analysis without the treatment variable, but with the interaction between treatment and time in the model controlled for. They argue that failure to control for baseline differences in outcomes between the groups can lead to biased treatment estimates. Alternatively, others have cautioned against this approach (Sen, 2013).

Based on our understanding of the literature, our analysis of impact on the primary outcome will be conducted using a fixed effects analysis of co-variance (ANCOVA) model, which accounts for the stratification factor used in randomisation.

We will use the following model:

$$Y_i = \beta_0 + \beta_1 Baseline_i + \beta_2 Group_i + \delta School_k + \varepsilon_i \in N(0, \sigma^2)$$

For i = 1, ..., n pupils per school, and k = 1, ..., K schools.

Where:

• Y_i is the school engagement subscale score as measured by the SCQ.

- *Baseline_i* is the baseline outcome measure of the school engagement subscale for pupil *i*.
- *Group*_i is a dummy variable for allocation group, i.e. 1 for the treatment group and 0 for the control group.
- β_2 is the average treatment effect, i.e. the primary parameter of interest for the trial.
- School_k is a vector of K 1 binary school dummy variables.
- ε_i is the error/residual.
- σ^2 is the variance.

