This analysis is designed to evaluate the differences in school engagement between boys in the BDP group, and boys in the business-as-usual group. Specifying the model upfront will ensure analysis avoids the "fishing problem" and the "curse of dimensionality" (Humphreys et al 2013; Hayes 2011).

We will run robustness checks to assess the underlying assumptions for ANCOVA. This will include assessing normality of the data using histograms and K-S tests. If the data does not meet these assumptions, we will run a non-parametric ANCOVA analysis. This will be determined once all data has been collected.

In line with the findings from Marsh and Randolph's (2020) original validation paper for the SCQ, it is possible that the baseline and outcome variables may be positively skewed. Skew will be assessed using the traditional criteria based on their distribution (i.e., skews of greater or equal to 1.0 or less than or equal to -1.0). Arguably, it is more desirable to use the appropriate modelling of non-normally distributed variables (e.g., Akram et al., 2023), than it is to transform the data.

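### Exclusions are assigned the questionnaire-score ANCOVA, whose normality switch would in practice replace it with an unnamed non-parametric analysis that gives no adjusted rate or risk effect

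*SAP*

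**What the plan says.** Section 3 of the SAP gives the programme's purpose as "to improve school engagement and reduce the likelihood of exclusion". Exclusion is neither a primary nor a secondary outcome. It appears in section 6.5, under the lead-in "We will conduct the following exploratory further analysis", as "Improvements to school attendance and reductions to exclusion as measured by school administrative data". The analysis is conditional: "If we are able to access school administrative data which is of sufficient high quality, consistency and comparability across schools". The method is one sentence: "This will follow the same model as set out for the primary and secondary outcomes analysis".

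The model referred to is in section 6.2. The primary analysis "will be conducted using a fixed effects analysis of co-variance (ANCOVA) model, which accounts for the stratification factor used in randomisation", with a normally distributed error. On checking, the section says: "This will include assessing normality of the data using histograms and K-S tests". It continues: "If the data does not meet these assumptions, we will run a non-parametric ANCOVA analysis". Section 6.3 repeats the check and the switch for the secondary outcomes. The non-parametric procedure is not named in either place. Section 6.12 expresses effects as Hedges' g, the adjusted ANCOVA mean difference divided by the pooled standard deviation.

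Two other statements bear on the point. Section 6.2 remarks that modelling a non-normal variable suitably is arguably better than transforming it, but names no distribution or link. Section 6.5 allows a generalized linear model for the dosage analysis and not for exclusions.

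**The concern.** An exclusion is an event. Whether it is recorded as a count or as yes/no, the variable takes few values, and it is likely to have many boys at zero. The section 6.2 route was written for questionnaire sums. Applied to exclusions, its normality check would be expected to fail, and the plan then states without qualification that a non-parametric ANCOVA will be run.

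Such a test can say whether the arms differ. It does not give an adjusted rate ratio, rate difference or risk difference with a confidence interval. Section 6.12 does not help, because its numerator is a difference in ANCOVA-adjusted means, and the plan does not say what replaces it after the switch. The programme's purpose is put in terms of how likely exclusion is, and the written route would not estimate that on an adjusted scale.

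**Working it through.** **1. The plan's own figure.** The SAP gives no figure for exclusions. Its power figure is for the questionnaire score (sections 5.1 and 5.2): N = 422, power 0.80, two-sided 0.05, correlation r = 0.7. With MDES = (t(0.975) + t(0.80)) × √[(1 − r²)/(0.25 N)]:

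(1.966 + 0.842) × √[0.51/(0.25 × 422)] = 2.808 × 0.0695 = 0.195.

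This matches the SAP, as does N = 424 (0.1948). It does not carry over to an exclusion variable.

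**2. Would the check fail?** If a share z of boys has zero exclusions, the observed distribution function jumps by z at that value. A continuous normal curve must therefore miss it by at least z/2 on one side. The usual large-sample 5% limit for the K-S statistic at N = 424 is about 1.36/√424 = 0.066. So any z above about 2 × 0.066 = 13% fails. A yes/no variable always fails, since its commoner value holds at least half the boys and the distance is at least 0.25. In simulations with 58.7% to 93.5% of boys at zero, K-S rejected normality in every run.

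**3. What follows for error rate and power?** Assumed inputs: 424 boys, six schools, 600 runs per scenario, baseline and school terms in every model, and a halving of exclusions as the effect. The SAP supplies none of the rates. A rank ANCOVA stands in for the unnamed fallback. Monte Carlo error is about √(0.25/600) = 2 points. μ is the mean number of exclusions per control boy and k the gamma shape (smaller k means more overdispersion).

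| Scenario | Linear ANCOVA | Rank ANCOVA | Robust Poisson | Rank minus Poisson (points) |
|---|---|---|---|---|
| μ 0.1, k 0.5 | 0.412 | 0.375 | 0.433 | −5.8 |
| μ 0.2, k 0.5 | 0.700 | 0.638 | 0.708 | −7.0 |
| μ 0.4, k 0.5 | 0.902 | 0.808 | 0.907 | −9.9 |
| μ 0.4, k 0.25 | 0.862 | 0.655 | 0.853 | −19.8 |
| μ 0.2, k 2 | 0.725 | 0.687 | 0.728 | −4.1 |
| μ 1.0, k 0.5 | 0.998 | 0.957 | 0.998 | −4.1 |
| μ 0.4, k 0.5, baseline unrelated | 0.858 | 0.770 | 0.867 | −9.7 |
| μ 0.4, k 0.15, baseline unrelated | 0.595 | 0.427 | 0.637 | −21.0 |
| Effect only on any exclusion, 10% of controls | 0.310 | 0.508 | 0.353 | +15.5 |
| Effect only on any exclusion, 20% of controls | 0.572 | 0.842 | 0.568 | +27.4 |

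In the first eight rows the effect multiplies the count. In the last two it changes only whether a boy is excluded, with heavy-tailed counts among those who are.

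With no effect, rejection rates across the scenarios were 3.5% to 5.2% for linear ANCOVA, 3.5% to 6.5% for the rank version and 4.0% to 7.8% for robust Poisson. Part of any Poisson advantage may therefore be mild inflation. A logistic model of any exclusion, run in the first six scenarios, had power 0.363 to 0.897, slightly below the rank version each time. Its benefit is the scale on which it reports, not power.

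**The case against.** The strongest reply is that the stakes are low. The analysis is exploratory and may never run, the trial's key question is school engagement, and section 6.2 shows that the authors had suitable modelling of non-normal variables in mind. All of that stands and sets the weight of the point. The remark in section 6.2 binds nothing, however, and it sits beside a switch stated as definite.

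Section 6.5 imports the model and does not repeat the check. That the check carries over is the natural reading, but it remains an inference.

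A reader might infer more than the SAP supports:

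- *That the planned analysis loses power.* Not in general: the sign depends on the form of the effect. The plan also does not say that its fallback is rank-based.
- *That linear ANCOVA of an exclusion variable is invalid.* It kept its error rate, and its power was within about 4 points of robust Poisson throughout. Its coefficient is an adjusted mean difference per boy, which multiplied by 100 is a difference per 100 boys.
- *That no exclusion rate could be reported.* Raw rates by arm can be described under any method. What the fallback drops is the adjusted effect and its interval.
- *That unequal follow-up distorts the comparison.* Entry was staggered: 116 boys had been onboarded by 4 January 2024, and baseline collection ended in February 2025. But section 6.5 states no window, the questionnaires use fixed times of 12 and 24 weeks, and the protocol may define one. Randomisation within school would also tend to balance time at risk.
- *That attendance is equally ill served.* The same sentence covers attendance, but nothing was shown for it.

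**Conclusion.** The point holds in a limited form. If the normality check carries over to section 6.5, exclusions will almost certainly be moved to an unnamed non-parametric ANCOVA, whose test gives no adjusted rate or risk effect. For a yes/no variable this needs no assumption about rates. For a count it needs only more than about 13% of boys at zero. The plan is also inconsistent in allowing a generalized linear model for dosage and not for exclusions.

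The loss is in what can be reported. No general loss of power and no inflated error rate is shown. The simulated differences (about 4 to 21 points lower, or about 15 to 27 higher) rest on assumed exclusion rates, dispersion, a halving of exclusions and a rank version of the fallback. Because the analysis is exploratory and conditional, this is a change to consider, and it does not affect the primary result.

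**What to change.** In section 6.5:

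- Define the exclusion variable and a fixed window after randomisation. If windows must differ, include an offset for days on roll.
- State that exclusions are exempt from the K-S switch and from Hedges' g.
- Name the analysis: any exclusion as an adjusted risk difference, the number of exclusions with a log-link count model and robust standard errors, or both. Use allocation, school and pre-randomisation exclusions as terms. If both are used, say beforehand which leads.
- Report the rate ratio (for the count) and the absolute difference per 100 boys, with confidence intervals.

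The cost is a few sentences and a different model procedure, with no new data beyond what section 6.5 already hopes to obtain. Section 6.1 promises that the analysis plan will be revisited once baseline data are complete, and the version history for 1.1 records only the section 5 update, so a further revision could carry it. The drawback is that exclusion results will not be in standard deviation units like the other outcomes. If exclusions prove very rare, the robust count model may reject slightly too often (up to 7.8% in the runs with no effect), which should be acknowledged when it is reported.
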